**3.2 How will adverse event data be collected/recorded?**

Paper AE forms/source documents

Spreadsheet: paper or electronic

**3.3. How will AEs be classified/graded?  Check all that apply**

Serious/Not serious  Required for all protocols

**3.4 What scale will the PI use when evaluating the relatedness of adverse events to the study participation?**

The PI will determine the relationship of adverse events to the study using the following scale:

Related:	AE is clearly related to the intervention
Possibly related:	AE may be related to the intervention
Unrelated:	AE is clearly not related to intervention

**3.5 When will recording/reporting of adverse events/unanticipated problems begin?**

After subject begins study drug/ device placement/intervention /study-related procedure/specimen collection

**3.6 When will the recording/reporting of adverse events/unanticipated problems end?**

Subject completes intervention and follow up period of protocol

**3.7 How will Adverse Events, Unanticipated Problems, Protocol Violations and Data Breaches be reported? Complete the table below to answer this question**

Type of Event	To whom will it be reported:	Time Frame for Reporting	How reported?
Any internal event resulting in death that is deemed DEFINITELY related to (caused by) study participation An internal event is one that occurs in a subject enrolled in a UVa protocol	IRB-HSR	Within 24 hours	IRB Online and phone call www.irb.virginia.edu/
Internal, Serious, related/possibly related Unexpected adverse event	IRB-HSR	Within 7 calendar days from the time the study team received knowledge of the event. Timeline includes submission of signed hardcopy of AE form.	IRB Online www.irb.virginia.edu/
Unanticipated Problems that are not adverse events or	IRB-HSR	Within 7 calendar days from the	Unanticipated Problem report form.

**IRB-HSR#18088:** Locally applied antibiotics for infection prophylaxis in treatment of open fractures

protocol violations This would include a Data Breach.		time the study team received knowledge of the event.	http://www.virginia.edu/vprgs/irb/HSR_docs/Forms/Reporting_Requirements-Unanticipated_Problems.doc )
Protocol Violations/Noncompliance The IRB-HSR only requires that MAJOR violation be reported, unless otherwise required by your sponsor, if applicable.  OR  Enrollment Exceptions See definition- only allowed if there is a commercial sponsor or a DSMB that has granted the enrollment exception.	IRB-HSR	Within 7 calendar days from the time the study team received knowledge of the event.	Protocol Violation, Noncompliance and Enrollment Exception Reporting Form  http://www.virginia.edu/vprgs/irb/hsr_foms.html  Go to 3rd bullet from the bottom.
Data Breach	The UVa Corporate Compliance and Privacy Office, a  ITC: if breach involves electronic data-  Police if breach includes items that are stolen:  Stolen on UVA Grounds  OR  Stolen off UVa Grounds- contact police department of jurisdiction of last known location of PHI	As soon as possible and no later than 24 hours from the time the incident is identified.  As soon as possible and no later than 24 hours from the time the incident is identified.  IMMEDIATELY.	UVa Corporate Compliance and Privacy Office- [contact]  ITC: Information Security Incident Reporting procedure , http://www.itc.virginia.edu/security/reporting.html  UVa Police-Phone- [contact]

**4. How will the endpoint data be collected/recorded.**

  X   Protocol specific case report forms

Source documents

Database:  Specify  Answer/Response:

Other:  Specify  Answer/Response: excel spreadsheet with de-identified data from other institutions will be combined with the excel spreadsheets at UVA. The University of Virginia will not be transferring data to other institutions, only receiving data.

## 5. Data and Safety Oversight Responsibility

### 5.1. Who is responsible for overseeing safety data for this study?

No additional oversight body other than PI at UVa  Skip question 5.2

All site PI's (*for protocols in which there is no common protocol but data from multiple sites will be combined for analysis: Collaborative Site Analysis Studies*)

The UVa Cancer Center Data and Safety Monitoring Committee

If your study involves cancer patients, see Question # 6 to help you decide if you should check this option.

Medical Monitor

This could include such things as the overall PI of a multisite trial.

DSMB/ DSMC

If your study is NIH funded, check with the center to determine if they require a DSMB for this study.

The following groups/individuals are NOT considered a DSMB:

DO NOT CHECK THIS BOX

- Members of the study team
- Medical monitors from a commercial drug company
- Safety review committee within a commercial drug company
- UVa Cancer Center Data and Safety Monitoring Committee
- The overall PI of a multi-site trial or a single individual who may serve as the medical monitor.

The following groups are considered a DSMB:

- A group of scientists, physicians, statisticians and others that are not employees of the commercial drug company that are appointed to oversee the data and safety of subjects in the study.
- A group of scientists, physicians, statisticians and others that are, or are not, employees of UVa, are not affiliated with the UVa study team, and are appointed to oversee the data and safety of the subjects in the study.

DSMB Charter Template

A template for a DSMB charter may be found on the IRB-HSR Website at [DSMB Charter Template](#).

Research Monitor:  Insert Name  Answer/Response:

Name required for protocols funded by the Department of Defense

Other:  Specify  Answer/Response:

**5.2. What is the composition of the reviewing body and how is it affiliated with the sponsor?**

Information may be found in the UVa Cancer Center Institutional DSMP  
 Collaborative Site Analysis Study- see CSAS section of this DSMP  
 Other: Specify Answer/Response:

**5.3. What items will be included in the aggregate review conducted by the PI?**

NA- PI is not the overall person overseeing the safety data for this study.  
 All adverse events  
 Unanticipated Problems  
 Protocol violations/Issues of noncompliance  
 Audit results  
 Application of dose finding escalation/de-escalation rules  
These should be outlined under 2.4.  
 Application of study designed stopping/decision rules  
 Early withdrawals  
 Whether the study accrual pattern warrants continuation/action  
 Endpoint data  
 Other: Specify Answer/Response:

**5.4 How often will aggregate review occur?**

For additional information on aggregate review see:

[www.virginia.edu/vpr/irb/hsr/continuations.html#aggreview](http://www.virginia.edu/vpr/irb/hsr/continuations.html#aggreview)

NA- PI is not the overall person overseeing the safety data for this study.  
 Per Enrollment/Events  
 Annually  
 Semi-Annually  
 Quarterly  
 Monthly  
 Other: Specify Answer/Response:

**5.5. How often will a report, regarding the outcome of the review by the DSMB/DSMC, be sent to the UVa PI?**

NA- PI is not the overall person overseeing the safety data for this study.  
 Per Enrollment/Events  
 Annually  
 Semi-Annually  
 Quarterly  
 Monthly  
 Other: Specify Answer/Response: N/A no DSMB

**5.6. How will a report of the information discussed in question 5.4 OR 5.5 be submitted to the IRB?**

Part of IRB-HSR continuation status form  
 Separate report from DSMB/DSMC or UVa PI  
 Other: **Specify** **Answer/Response:**

### Risk/ Benefit Analysis

**1. What are the potential benefits for the participant as well as benefits which may accrue to society in general, as a result of this study?**

Decreased infection rates, decreased re-admission to hospital and repeat surgery, decreased time to union, decreased pain and recovery time of patient, decreased morbidity associated with open fractures. The benefits to the society are immense. This avenue of research has the potential to bring down the cost of antibiotic treatment, avoid the negative side effects of the antibiotics such as nephrotoxicity and ototoxicity in people with kidney disease, and improved delivery of drug to the wound site.

**2. Do the anticipated benefits justify asking subjects to undertake the risks?**

Yes. The risk-benefit analysis is acceptable.

## **APPENDIX: Legal/Regulatory**

### **Recruitment**

The following procedures will be followed:

- Finders fees will not be paid to an individual as they are not allowed by UVa Policy.
- All recruitment materials will be approved by the IRB-HSR prior to use. They will be submitted to the IRB after the IRB-HSR has assigned an IRB-HSR # to the protocol.
- Only those individuals listed as personnel on this protocol will recruit and or conduct the consenting process with potential subjects.

### **Retention Incentives**

Any item used by the sponsor/ study team to provide incentive to a subject to remain in the study, other than compensation identified in the Payment section, will be submitted to the IRB for review prior to use. The IRB-HSR will provide the study team with a Receipt Acknowledgement for their records. Retention incentive items are such things as water bottles, small tote bags, birthday cards etc. Cash and gift cards are not allowed as retention incentives.

### **Clinical Privileges**

The following procedures will be followed:

- Investigators who are members of the clinical staff at the University of Virginia Medical Center must have the appropriate credentials and been granted clinical privileges to perform specific clinical procedures whether those procedures are experimental or standard.
- The IRB cannot grant clinical privileges.
- Performing procedures which are outside the scope of the clinical privileges that have been granted may result in denial of insurance coverage should claims of negligence or malpractice arise.
- Personnel on this protocol will have the appropriate credentials and clinical privileges in place before performing any procedures required by this protocol.
- Contact the Clinical Staff Office- [name] or [name] for further information.

### **Sharing of Data/Specimens**

Data and specimens collected under an IRB approved protocol are the property of the University of Virginia. You must have "permission" to share data/ specimens outside of UVa other than for a grant application and or publication. This "permission" may come in the form of a contract with the sponsor or a material transfer agreement (MTA) with others. A contract/ MTA is needed to share the data outside of UVa even if the data includes no HIPAA identifiers and no code that could link the data back to a HIPAA identifier.

- No data will be shared outside of UVa, beyond using data for a grant application and or publication, without a signed contract/MTA approved by the SOM Grants and Contracts office/ OSP or written confirmation that one is not needed.
- No specimens will be shared outside of UVa without a signed contract/MTA approved by the SOM Grants and Contracts office/ OSP or written confirmation that one is not needed.

### **Prisoners**

If the original protocol/ IRB application stated that no prisoners would be enrolled in this study and subsequently a subject becomes a prisoner, the study team must notify the IRB immediately. The study team and IRB will need to determine if the subject will remain in the study. If the subject will remain in the study, the protocol will have to be re-reviewed with the input of a prisoner advocate. The prisoner advocate will also have to be involved in the review of future continuations, modifications or any other reporting such as protocol violations or adverse events.

**Prisoner-** Individuals are prisoners if they are in any kind of penal institution, such as a prison, jail, or juvenile offender facility, and their ability to leave the institution is restricted. Prisoners may be convicted felons, or may be untried persons who are detained pending judicial action, for example, arraignment or trial.

For additional information see the OHRP website at <http://www.hhs.gov/ohrp/policy/populations/index.html>

### **Compensation in Case of Injury**

If a subject requests compensation for an injury, the study team should notify the IRB-HSR ([name]) the UVa Health System Patient Relations Department ([name]). As a proactive courtesy, the study team may also notify UVa Health System Patient Safety and Risk Management ([name]).

On request, the study team should provide the Risk Management Office with the following information/documents:

- Subject Name and Medical Record Number
- Research medical records
- Research consent form
- Adverse event report to IRB
- Any letter from IRB to OHRP

### **Subject Complaints**

During a research study, the study team may receive complaints from a subject. If the study team is uncertain how to respond to a complaint, or is unable to resolve it with the subject, the study team may contact the IRB-HSR ([name]), the UVa Health System Patient Relations Department ([name]).

### **Request for Research Records from Search Warrant or Subpoena**

If the study team receives a request for research records from a search warrant or subpoena, they should notify UVa Health Information Services at [name]. It is important to notify them if information from the study is protected by a Certificate of Confidentiality.

## APPENDIX: Safeguards for Cognitively Impaired

### 1. What additional safeguards that will be employed to protect the cognitively impaired subjects?

Use of Surrogate decision-maker when permitted by law, i.e. a legally authorized representative via use of power of attorney/advance directive for research.

### 2. The following steps will be taken to determine the capacity of a potential subject to give consent for themselves.

A. If there is concern that a potential subject/ subject may be cognitively impaired a determination of incompetence will be made after an evaluation by a person with the appropriate expertise to make such a determination as delegated by the PI. If the subject is a patient in the UVa Medical Center, the [Medical Center Policy No. 0024](#) will also be followed. The determination of competency must be documented in writing.

B. The following methods below will be used to determine capacity for consent:

Subject is also a patient in the UVa Medical Center and [Medical Center Policy No. 0024](#) will be followed.

Will rely on individual observation of and interaction with the potential subject as well as the opinion of the medical provider or caregiver, when available. The prospective subject should demonstrate competence in relation to the proposed study in order to be judged capable of providing informed consent for that study. In general, an assessment an individual's capacity to consent will be based on her/his:

- Ability to communicate a choice;
- Ability to understand relevant information;
- Ability to appreciate the nature of the situation and its likely consequences; and,
- Ability to manipulate information rationally (1)

C. An individual will be considered unable to provide consent if he or she has:

- An inability to express or communicate a preference or choice (cannot make up his/her mind, is comatose, or has severe psychotic thought disorders, etc.);
- An inability to understand a situation and its potential consequences as well as the impact of study participation on those circumstances (does not understand that he/she may be hurt or may not be helped or cannot distinguish research from treatment); and/or,
- An inability to provide a logical rationale for participation/no participation in a study (cannot address risk/benefit-related reasons for or against participation in a study).

### 3. The following steps will be taken to document the determination of competency to consent.

A note to file will be written and filed in the study files and/or medical records to describe the consenting process. The note will include a description of methods used to determine capacity

of the subject to consent. The note should also include the name of the person determining competency of the subject. May use the SOM CTO form [Determination of Capacity to Consent](#).

**4. When will subjects capacity to consent be assessed?**

Prior to initial consenting process if there is a concern that the potential subject has a cognitive impairment. Must be checked for all protocols.

On a periodic basis throughout the study process if there is a concern that the potential subject has a cognitive impairment. Must be checked if the study is ongoing and there is the possibility that the subject may regain their cognitive ability and be able to consent for themselves.

**5. Will UVa researcher conduct the study outside the state of Virginia? NO**

**6. Are you requesting the use of a Legally Authorized Representative? YES**

► **IF YES, do you confirm that this study includes none of the following which are conditions which limit the use of an LAR in Virginia?**

1. non-therapeutic research unless it is determined by the human research committee (IRB) that such non-therapeutic research will present no more than a minor increase over minimal risk to the human subject.
2. participation in human research on behalf of a prospective subject if the legally authorized representative knows, or upon reasonable inquiry ought to know, that any aspect of the human research protocol is contrary to the religious beliefs or basic values of the prospective subject, whether expressed orally or in writing.
3. participation in human research involving non-therapeutic sterilization, abortion, psychosurgery or admission for research purposes to a facility or hospital as defined by the Code of Virginia at § [37.1-1](#).

Answer/Response: YES

## APPENDIX: Drug Information

**1. What is the drug name, manufacturer and IND# if available?**

Tobramycin injectable 80mg/2ml,  
Hospira at this time, but subject to change.

**2. If IND application has been submitted to the FDA, who is the Principal Investigator on the IND?**  
SOM CTO review on file-IND exempt

**3. What is the phase or stage of this study? Phase 3**

## APPENDIX: Pharmacy-Investigational Drugs/Biologics

**1. What is the name of the investigational drug/biologic?**

tobramycin

**2. Where will the subjects be seen for the administration/dispensing of the drug?**

Inpatient Unit: In the operating room

**3. What dose will be utilized in this study?**

Trobramycin 80mg/40mL

**4. What will be the frequency of dosing in this study?**

Once. The second dose that will be given will be the same randomization treatment as the first injection.

**5. What will be the duration of dosing in this study?**

Once dose administered over 1 minute

**6. What route of administration will be utilized?**

Injection into a closed wound/subcutaneous tissue

**7. Will drug need to be prepared by the UVa Investigational Drug Service (IDS)?**

Investigational pharmacy will store the drug and perform the randomization to drug or placebo, and provide the drug to the surgeons on the day of surgery. The randomization code will be stored by the **IDS Pharmacy** on a spreadsheet.

**8. Are there any special handling instructions mandated by the study (e.g. weighing hazardous materials)?**

No

**9. Does the protocol provide provisions for dose titration, dose reductions, and or re-challenged (if drug is stopped), etc.? No**

**10. How will missed doses be handled? n/a**

**11. Will a comparator (active or placebo) be utilized in the protocol? Yes**

► IF YES, comparator is: Placebo: 0.9% Normal Saline injection of 40mL

**12. Does this study involve research on a drug, biologic, supplement or food additive? Yes**

► IF YES, is this study investigator initiated? Yes

IF YES, answer questions # 13 and 14

IF NO, answer question # 13 only

**13 Are you using a drug/supplement/ food additive in a manner not approved by the FDA? Yes**

IF YES, answer questions 13a-13f

You may reference the non-IRB protocol to answer these questions.

**13a. Describe pertinent animal data that is available regarding the toxicity/safety of this drug.**

[name], Baum EJ, Dahmers LE. *Locally administered antibiotics for prophylaxis against surgical wound infection. An in vivo study.* J Bone Joint Surg Am. 2008 Feb;90 (2):384.

A 2008 study published by the PI in this study used a rat model, in which they inoculated a surgical wound in the quadriceps muscle with  $8.0 \times 10(5)$  colony-forming units of *Staphylococcus aureus* and then administered one of seven types of treatment: no treatment (control), bacitracin irrigation, calcium sulfate flakes, systemic gentamicin, local aqueous gentamicin, local gentamicin-loaded calcium sulfate flakes, and a combination of local gentamicin-loaded calcium sulfate and systemic gentamicin. The seven treatment groups consisted of ten rats each. To further evaluate a trend, the group treated with systemic gentamicin and the one treated with local gentamicin solution were extended to include twenty-five and twenty-seven rats, respectively. At forty-eight hours postoperatively, specimens from the wounds were obtained for quantitative cultured. They found that the control group, the group treated with bacitracin irrigation, and the one treated with plain calcium sulfate had very high bacterial counts and high mortality rates while the groups treated with gentamicin had low bacterial counts and a 100% survival rate. Local gentamicin was significantly more effective than systemic gentamicin in reducing bacterial counts.

**13b. Describe pertinent human data that is available regarding the toxicity/safety of this drug.**

From a patient safety standpoint, this drug has been shown to be appropriate for use locally based on cell culture data. The 2mg/ml concentration of aminoglycoside injected into the wounds after closure is high enough to decrease replication of osteoblasts, though not to cause cell death, at sustained concentrations *in vitro* . *In vivo*, this concentration decreases quickly as it diffuses.

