### SAFETY SUMMARY:

- Local tissue safety: 80mg/40mL is 2 mg/mL (which is 2000 micrograms / mL). This level was found to be safe in Rathbone/Wenke study (1). Further, the local level is expected to decrease quickly, as opposed to the sustained levels seen in tissue culture in that study.
- Systemic safety: Gentamicin/tobramycin is routinely given as a single IV dose at 4-7mg/kg (depending on severity of infection). For a 70kg patient treated with 5mg/kg dose, 350mg would be given IV (thus immediately available systemically). The dose we administer is only 80mg, a much lower dose, and is administered in the wound (thus more similar to IM than IV). Peak levels are not routinely checked at UVA for short courses of even the higher doses of IV tobramycin/gentamicin, and we find no safety issue or support for obtaining peak levels in this study. Systemic levels high enough to cause side effects are typically associated with dosing that is higher than recommended or too frequent to allow adequate renal clearance.
- In cases of renal impairment, dosing is typically spaced out further to allow time for renal clearance (see attached below from Stanford Guidelines 2013). This would not create a safety issue in our study, as a single 80mg dose is administered. If ongoing therapy with a systemic aminoglycoside is required (either gentamicin or tobramycin), the patient's primary team would be made aware of the intra-operative dose and follow serum levels as appropriate based on repeated dosing.
- This route of administration of local tobramycin represents the current standard of care in my practice. I have treated all open fractures this way since starting at UVA in 2012, and have observed no adverse effects. In fact, my impression is that the infection rate is lower as a result of this practice.

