**2. What are the statistical considerations for the protocol?**

- This is a prospective, randomized double blind study. Subjects will be randomized to antibiotic (80mg tobramycin/40mL saline) or placebo arm (40mL of 0.9% saline).
- The primary objective of this study is to evaluate the efficacy of local antibiotics in decreasing incidence of infection. The primary outcome will include evidence of infection in the first 6 weeks of surgery. Infection will be defined as major and minor, with major indicated by return to the operating room for irrigation and debridement. Minor infection is represented by documentation of cellulitis or superficial infection at surgical site and administration of oral antibiotics. .
- Superficial infection as indicated by documentation of cellulitis at surgical site and administration of oral antibiotics with the indication of wound problems. The primary purpose of this study is to document infection rates in the first 6 weeks after surgery. If an infection is found, it will be cared for per standard clinical care; however, it will not be followed for research purposes.
- There will be no contingencies for early stopping as the patients are receiving a single dose of antibiotics. There will be no interim analysis or stratification factors
- We expect approximately - 60 – 65 open fractures within a year to be treated at UVA based on historical records.

We will use a one-sided test for proportions to compare the control and experimental groups for the primary endpoint (presence of infection) and the secondary endpoint of evidence of non-union. A p-value less than 0.05 will be considered a significant result.

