**3. Provide a justification for the sample size used in this protocol.**

A sample size analysis was completed for different alpha and power levels. A one-sided test for proportions was chosen to compare the baseline (no treatment) group to the hypothesized proportion (treatment group); based on historical data, we assumed that the no treatment group would have a 10% infection rate, and the treatment group would have a 1% infection rate. Using an alpha of 0.05 and power of 70%, we would need to have 60 patients in each group.

With an expected accrual rate of 65 patients per year, we would expect to enroll 130 patients in two years. In order to maintain the sample size needed to ensure statistically valid results, we would want to enroll approximately 133 patients over the study period to end up with at least 120 patients in the analysis.

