## 2. Identified risks and plans to minimize risk

### 2.1 What risks are expected due to the intervention in this protocol?

Expected Risks related to study participation.	Frequency
Nephrotoxicity	 Occurs frequently  Occurs infrequently  Occurs rarely  Frequency unknown
Neurotoxicity manifested by ototoxicity – vestibular and auditory	 Occurs frequently  Occurs infrequently  Occurs rarely  Frequency unknown
Neurotoxicity manifested by numbness, skin tingling, muscle twitching and convulsions (in patients with preexisting renal damage and normal renal function with prolonged exposure to tobramycin)	 Occurs frequently  Occurs infrequently  Occurs rarely  Frequency unknown
Nephrotoxicity in patients with impaired renal function and in those who received high dose of tobramycin for prolonged period	 Occurs frequently  Occurs infrequently  Occurs rarely  Frequency unknown
Violation of subject's privacy and confidentiality	Minimized due to the requirements of the privacy plan in this protocol

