**14. Do the following criteria apply? Check all that apply**

The investigation is intended to be reported to FDA as a well-controlled study in support of a new indication for use or intended to be used to support any other significant change in the labeling for the drug;

If the drug that is undergoing investigation is lawfully marketed as a prescription drug product, the investigation is intended to support a significant change in the advertising for the product;

The investigation does involve a route of administration or dosage level or use in a patient population or other factor that significantly increases the risks (or decreases the acceptability of the risks) associated with the use of the drug product.

If Not checked- explain why you believe the risk to subjects is not increased:

tobramycin has long been used in treatment and prophylactic regimens in humans; the dose used in this experiment has been proven on a cellular level in animal models to be non-toxic and effective in prophylaxis against infection.

The investigation will be conducted in compliance with the requirements for institutional review set part in part 21CFR56 and with the requirements for informed consent set forth in part 21CFR50 ; and

The investigation will be conducted in compliance with the requirements of 21CFR312.7 (Promotion and charging for investigational drugs)

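### Non-union is assigned a one-sided test that, read towards benefit, cannot declare an excess on tobramycin, although the plan's own drug appendix makes impaired bone healing a plausible (unproven) local harm

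*Combined protocol and SAP*

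**What the plan says.** - **Cell data.** Appendix: Pharmacy-Investigational Drugs/Biologics, 13b, describes 2 mg/mL aminoglycoside as "high enough to decrease replication of osteoblasts, though not to cause cell death, at sustained concentrations" in vitro. It then says that the concentration drops quickly in the body by diffusion. Biomedical Research item 1 includes the fracture site among the tissues injected.
- **Safety statements.** The Safety Summary says of 2 mg/mL "This level was found to be safe", and adds that the local level should fall quickly, unlike in tissue culture. Item 14 of the same appendix says without that caveat that the dose "has been proven on a cellular level in animal models to be non-toxic".
- **Animal data.** The rat study in 13a used gentamicin in a contaminated quadriceps wound, with cultures at 48 hours. The findings reported are bacterial counts and survival, for example "Local gentamicin was significantly more effective than systemic gentamicin in reducing bacterial counts".
- **Analysis.** Statistical Considerations item 2 applies a one-sided test for proportions at p < 0.05 to infection and to "the secondary endpoint of evidence of non-union". Item 5 of the same section answers that secondary analysis is not applicable because only a primary analysis is done.
- **Risks.** The table headed "Expected Risks related to study participation" (Data and Safety Monitoring Plan 2.1) lists kidney toxicity, neurotoxicity including ototoxicity, and privacy. It has no bone-healing item. Section 3.1 records only adverse events judged related or possibly related.
- **Follow-up.** Clinic visits are at 2 and 6 weeks. Medical records are reviewed up to 1 year (Biomedical Research item 2).

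**The concern.** The documents themselves raise a local harm, reduced osteoblast replication, and the drug goes into the fracture site. The only planned comparison that touches bone healing is the non-union test. Its direction is not stated separately, but the Brief Summary, the Hypothesis and the sample size section all look for benefit. A one-sided test towards benefit has its whole rejection region on the side where tobramycin has fewer non-unions. However large an excess on tobramycin, the result would be reported as not significant.

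At stake is the balance of benefit and harm. The trial could report fewer infections and no significant difference in non-union while non-union was materially more frequent on tobramycin. The contradiction between items 2 and 5 adds a second route to the same gap, because non-union might not be analysed at all.

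**Working it through.** **1. Reproduce the plan's own figure.** Inputs, from Statistical Considerations item 3: "we assumed that the no treatment group would have a 10% infection rate, and the treatment group would have a 1% infection rate" and "Using an alpha of 0.05 and power of 70%, we would need to have 60 patients in each group". For a one-sided test with pooled variance and no continuity correction,

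n = [z(0.95)·√(2p̄(1−p̄)) + z(0.70)·√(p₁(1−p₁) + p₂(1−p₂))]² / (p₁−p₂)²

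With p₁ = 0.10, p₂ = 0.01, p̄ = 0.055:

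n = [1.645 × 0.3224 + 0.5244 × 0.3161]² / 0.09² = 59.8, so 60 per arm (power 70.1%).

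The stated 60 is reproduced. It was sized for infection; the documents give no rate, definition, assessment time or power for non-union.

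**2. What the one-sided test reports when tobramycin is worse.** Assumed counts, for illustration only: non-union in 3/60 on placebo and 12/60 on tobramycin.

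- Difference: 12/60 − 3/60 = 0.20 − 0.05 = +0.15.
- One-sided Fisher test towards benefit: p = 0.998.
- Two-sided Fisher test: p = 0.025.
- Standard error: √(0.05×0.95/60 + 0.20×0.80/60) = 0.0588.
- Wald 95% CI: 0.15 ± 1.96 × 0.0588 = +0.035 to +0.265.

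The same data read as not significant under the one-sided rule and as an excess of 3.5 to 26.5 points under the two-sided interval.

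**3. What two-sided testing could and could not show.** Assumed true rates, two-sided 5% level, exact binomial enumeration. The figure is the probability of declaring an excess on tobramycin. The 53 per arm is what the stated 20% loss would leave: 133 × 0.8 = 106.4.

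| Placebo vs tobramycin | 60 per arm, pooled z | 60 per arm, Fisher | 53 per arm, pooled z |
|---|---|---|---|
| 5% vs 10% | 17% | 9% | 15% |
| 10% vs 20% | 33% | 25% | 30% |
| 10% vs 25% | 58% | 49% | 54% |
| 5% vs 20% | 73% | 63% | 67% |

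For the one-sided benefit test this probability is zero in every row. For 80% two-sided power (normal approximation), 5% versus 10% needs 435 per arm and 10% versus 20% needs 199.

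The expected half-width of the 95% interval at 60 per arm is 1.96·√(p₁(1−p₁)/60 + p₂(1−p₂)/60):

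- 5% versus 10%: 9.4 points.
- 10% versus 20%: 12.7 points.

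**4. The safety statements side by side.** 13b reports reduced osteoblast replication in cell culture. Item 14 claims no toxicity at the cellular level, citing animal models. The animal study described in 13a used a different aminoglycoside and, as described, has no bone outcome, so it does not support item 14 on this point. The Safety Summary carries its own caveat about rapid decline and can be read consistently with 13b. Item 14 cannot.

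**The case against.** The strongest reply is that the authors considered bone toxicity and gave reasons to discount it. 13b limits the effect to sustained in-vitro exposure without cell death and speaks of aminoglycosides generally. The Background places tobramycin among the least cytotoxic agents and notes that the cell measurements were made at 10 and 14 days. This stands. A reader might infer that the injected dose suppresses osteoblasts in patients; the documents do not say so. But an expectation that harm is unlikely does not justify a test that cannot show it.

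A reader might also infer that slower or failed healing could not be detected at all. That goes too far:

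- The direction of the non-union test is inferred, not stated.
- Counts by arm would still show 3 against 12.
- A non-union judged possibly related could be recorded as an adverse event.
- Slower healing, measured as time to union, has no test of any kind, so sidedness is not its problem.

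Finally, one-sidedness is not the only obstacle. Item 5 removes secondary analysis, non-union is undefined, clinic visits end at 6 weeks, and a two-sided test would still usually miss a doubling. This also stands. It is why the remedy is an interval with a definition and a time point, and not merely a two-sided p-value.

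**Conclusion.** The point holds in a limited form. Impaired bone healing is a plausible, unproven harm on the plan's own evidence. The formal test named for non-union, read in the direction that every stated aim implies, cannot declare that harm, and another item says that no such analysis will be run. In the illustration this turns a two-sided p of 0.025 and an interval of +3.5 to +26.5 points into a one-sided p of 0.998.

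The illustration rests on assumed counts and on 60 analysed per arm. For smaller excesses the gain is in honest reporting more than in detection, since power against a doubling is about 9% to 33% depending on the rates and the test. The wording conflict on cellular toxicity is between 13b and item 14. The finding does not show that tobramycin delays union, and it leaves the primary analysis and its sample size untouched.

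**What to change.** 1. **Statistical Considerations items 2 and 5.** Reconcile them so that non-union is analysed. Replace its one-sided test with the difference in proportions by arm and a two-sided 95% CI, read as a safety outcome.
2. **Definition.** State what counts as non-union and at what time, within the record review already planned to 1 year.
3. **Interpretation.** Say in advance that the interval will be wide and that a non-significant difference is not evidence of no harm.
4. **Safety text.** Reconcile item 14 with 13b. State that the animal study in 13a used gentamicin and reports no bone outcome.
5. **Risk table (2.1).** Add an entry on bone healing that carries the in-vitro limitation.

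Cost: no extra patients or visits, and no change to the primary sample size. A claim of benefit on non-union would face a two-sided bar. A non-union data field is needed, including at the collaborating sites if their data are pooled, because union is not in the list of information they will send. No imaging is done for research, so the definition has to work from routine records.
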